#### **D.4. SMAART (Specific Aims 1 and 2):**

- To evaluate whether a polypill-based treatment strategy vs. usual care will result in carotid intimal media thickness stabilization/regression among recent stroke patients at one year after an index ischemic stroke. (Aim 1)
- To evaluate whether a polypill-based treatment strategy vs. usual care will improve vascular risk reduction drug adherence and tolerability among recent stroke patients at one year after an index ischemic stroke. (Aim 2)

**D.4.1. Study Design:** SMAART is a phase II randomized, open label, blinded endpoint clinical trial to evaluate the effect of a polypill taken once daily orally in improving CMIT regression and adherence to secondary risk reduction drug intake vs. 'usual care' group with separate individual secondary preventive medications among Ghanaians with recent onset stroke/TIA in a single center study.

**D.4.2. Participants:** The participants will include 120 adult Ghanaian recent stroke/TIA patients (within two months of stroke onset) meeting inclusion/exclusion criteria who will be randomly assigned to either intervention or usual care arms.

**D.4.3. Inclusion Criteria:** 1. Above the age of 18 years; male or female; 2. Stroke/TIA diagnosis no greater than two months before enrollment. Ischemic strokes including lacunar, large-vessel atherosclerotic, cardio-embolic subtypes are eligible 3. Subjects with stroke may present with at least one of the following additional conditions: Documented diabetes mellitus or previous treatment with oral hypoglycemic or insulin; documented hypertension >140/90mmHg or previous treatment with anti-hypertensive medications; Mild to moderate renal dysfunction (eGFR 60-30ml/min/1.73m^2); Prior myocardial infarction 4. Legally competent to sign informed consent.

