**D.4.4. Exclusion criteria:** 1. Unable to sign informed consent, 2. Contraindications to any of the components of the polypill, 3. Hemorrhagic stroke, 4. Severe cognitive impairment/dementia or severe global disability limiting the capacity of self-care, 5. Severe congestive cardiac failure (NYHA III-IV), 6. Severe renal disease, eGFR <30ml/min/1.73m^2), renal dialysis; awaiting renal transplant or transplant recipient, 7. Cancer diagnosis or treatment in past 2 years, 8. Need for oral anticoagulation at the time of randomization or planned in the future months, 9. Significant arrhythmias (including unresolved ventricular arrhythmias or atrial fibrillation) 10. Nursing/pregnant mothers, 11. Do not agree to the filing, forwarding and use of his/her pseudonymized data.

**D.4.5. Recruitment of study subjects:** A total number of 120 patients will be randomized (1:1) to treatment arms. Patients with stroke meeting inclusion/exclusion criteria will be recruited from the Family Medicine, Internal Medicine and Neurology outpatient clinics at KATH. Randomization will take place within 8 weeks of the index event (ischemic stroke) in a 1:1 ratio to one of the two arms: Polypill versus Usual care.

**D.4.6. Randomization Procedure:** Randomization of subjects in blocks of four will be conducted by a statistician ([name] PI) using a computer-generated random sequence of numbers. Consented participants will be assigned to either study arm at the baseline visit using the computer generated randomization sequence. The randomization sequence uses a minimization algorithm to ensure balance of prognostic factors such as stroke severity, average of 3 recorded baseline systolic BP measurements, & whether or not they are on background BP lowering agents, lipid modifiers & antithrombotic agents. Each sequence generated will be kept concealed in an envelope which will be opened by the Research Coordinator in the presence of the consenting study participant at enrollment.

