CVD Risk Factor Control Tertiary/feasibility	1. Blood pressure control will be defined as Systolic BP <140 mmHg and/or diastolic DP <90mmHg or (>135/85mmHg in diabetes patients). Mean change in SBP at month 12 from baseline will be compared in the two treatment groups. 2. Dyslipidemia: control will be defined by change in mean LDL-cholesterol <100mg/dl or <70mg/dl. Mean change in LDL-C at month 12 from baseline will be compared in the two treatment groups.
Incidence of Adverse events Tertiary/feasibility	1. Recurrent stroke: fatal/ severely disabling stroke or non-fatal stroke; Coronary Artery Disease: Acute STEMI/NSTE deaths 2. Re-hospitalization for any CV cause; All-cause mortality

**D.4.9. Sample size justification:** The end of study CIMT value will be subtracted from the baseline CIMT value and divided by the length of follow-up. The rate of change in CIMT (mm/yr) between treatment arms will be tested with a two sided t-test. The rate of change in common CIMT in treated patients is around 0.085 mm/yr with a standard deviation of 0.035. We assume that polypill improvement leads to a halting of CIMT progression with an assumed rate of change of 0.0825 mm/yr. With a two sided alpha of 0.05 and a 90% power we need 82 patients (104 patients with 20% drop-out rate).

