**D.4.10. Statistical analysis plan:** Prior to addressing each hypothesis, univariate descriptive statistics and frequency distributions will be calculated as appropriate for all biological variables (including gender, age) comparing individuals by treatment arms (Polypill arm vs usual care arm). Briefly, box plots will be used to examine the relative distribution of variables stratified by treatment arm. Non-parametric and equivalent parametric statistics will be utilized to compare groups. Appropriate regression models (linear regression for continuous outcomes such as carotid-media thickness; Cox-proportional hazards regression for time to event measures such as recurrent strokes, CVD events, deaths and defaults) will be used to estimate the association of covariates with each outcome. When building models for each specific aim, the first stage of the model building algorithm will involve testing if the individual covariates are correlated with the main outcome variables. A liberal alpha=0.20 will be used for these unadjusted analyses. Once the initial pool of candidate predictors has been identified, regression models consisting of multiple covariates will be fitted to identify potential confounders and effect modifiers. To achieve unbiased and robust results, optimal combinations of predictors, including interaction effects, will be identified and used for further analysis based upon whether or not they are a confounder, by whether they did not improve the model fit, or increased the standard error of the parameter estimate of the primary covariates. Finally, each model will be rigorously assessed for collinearity and goodness of fit using residual analysis. Model diagnostics will be performed using tools (in SAS or STATA) that detect outliers and influential data points. We will use diagnostic measures such as residual deviance, the hat matrix diagonal and residual chi-squared deviance and the difference between chi-square goodness-of-fit when an observation is deleted. Plots of these against predicted values will be used to investigate the influence of each data point on the model. We will handle missing data using several techniques including multiple imputation and propensity score methods.

**D.4.11. Data Safety Monitoring Board (DSMB):** A DSMB comprised of three experienced external experts will meet twice per year to review the safety, ethics, and outcomes of the study.

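### No passage says whether the t-test in D.4.9 or the data-selected regression in D.4.10 is the CIMT result that answers Aim 1

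*Combined protocol and SAP*

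**What the plan says.** Aim 1 in D.4 is a comparison of arms: "To evaluate whether a polypill-based treatment strategy vs. usual care will result in carotid intimal media thickness stabilization/regression". Table 1 labels CIMT the primary outcome and defines it as a rate of change in mm per year, but names no test.

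The test appears in D.4.9, the sample size section: "The rate of change in CIMT (mm/yr) between treatment arms will be tested with a two sided t-test". The alpha of 0.05, the 90% power and the figure of 82 patients are attached to it. It is not called the primary analysis.

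D.4.10 does not mention a t-test. One sentence says that groups will be compared with parametric and non-parametric statistics, without naming an outcome, a test or a priority. Regression models follow, linear for CIMT, which "will be used to estimate the association of covariates with each outcome". Selection then proceeds in stages. "When building models for each specific aim, the first stage of the model building algorithm will involve testing if the individual covariates are correlated". That screen is run against the outcome at a liberal alpha of 0.20. After that, "optimal combinations of predictors, including interaction effects, will be identified and used for further analysis based upon whether or not they are a confounder", or by whether "they did not improve the model fit, or increased the standard error of the parameter estimate of the primary covariates". The term primary covariates is not defined, and treatment arm is never named as a model term.

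On allocation, D.4.6 says both "Randomization of subjects in blocks of four will be conducted by a statistician" and "The randomization sequence uses a minimization algorithm to ensure balance of prognostic factors such as stroke severity". It goes on to name baseline systolic pressure and background use of three drug classes, which makes five factors in an open list.

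**The concern.** The section headed as the analysis plan should state which CIMT comparison decides Aim 1. Here the only named test of the arm difference sits in the sample size section, and the plan itself describes a different kind of analysis whose final form depends on the trial data. The selection is to be done for each specific aim, so it reaches Aim 1.

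Two things are at stake. If the selected model supplies the treatment p-value, or if either result may be reported as the finding, the nominal 5% error rate is no longer guaranteed. Also, B.2 says the trial is to inform a phase 3 design, and a reader of the results could not tell which CIMT estimate had been planned. The sonographers are blinded to arm (D.4.7.5), which protects the measurements but does not restrict a later choice of model.

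**Working it through.** **1. The plan's own figure.** Inputs from D.4.9: SD 0.035, two-sided alpha 0.05, power 90%, rates 0.085 and 0.0825 mm/yr. The formula is n per arm = 2 × [SD × (1.960 + 1.282) / difference]².

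- Printed difference 0.085 − 0.0825 = 0.0025: 4,119 per arm, 8,238 in total. The stated 82 is not reproduced.
- Difference 0.025: 41.19 per arm, 82.4 in total, which matches 82. Dropout: 41 / 0.8 = 51.25, so 52 per arm and 104 in total, as stated.

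The mismatch is a separate matter. It is shown only because the power figures in step 4 use 0.025, that is 0.025 / 0.035 = 0.714 SD.

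**2. The text.** D.4.9 names a test and gives it no rank. D.4.10 gives a regression and does not name the test. Table 1 gives the outcome and no test. No sentence ranks the two analyses.

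**3. What the missing ranking could cost.** Null simulations used blocks of four and a normal outcome, mostly with 82 analysed patients and in one set also 96 (120 × 0.8). The documents do not give the number or strength of candidate covariates. These are assumptions: 5 to 20 independent candidates, total R² from 0 to 0.3. The algorithm was a screen at p<0.20, then backward selection at p<0.05 and/or by standard error, with the arm always in the model. The confounder rule, for which D.4.10 gives no threshold, was set to keep a covariate whose removal moves the arm estimate by more than 10%. Runs had 4,000 to 20,000 replicates (Monte Carlo SE about 0.16 points at 20,000 and 0.35 to 0.5 at 4,000). Type I error at nominal 5%, as the range over all settings and runs:

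| Source of the treatment p-value | With confounder rule | Without it |
|---|---|---|
| t-test alone | 4.7–5.4% | same |
| Fixed covariates | 4.7–5.5% | same |
| 0.20 screen only | not applicable | 4.6–5.7% |
| Selected model | 4.9–6.5% | 5.1–9.1% |
| Either t-test or selected model | 5.6–9.3% | 5.2–10.5% |

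The upper ends without the rule need 20 candidates and R² of 0.3. Selection by fit and selection by standard error give nearly the same result, so the inflation comes from data-driven selection in general.

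**4. What a fixed adjusted model costs or gains.**

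- *Covariate cost.* With baseline CIMT and five factors (k = 6), none prognostic, under blocks, expected variance rises by (n − 3) / (n − 3 − k). This is 79/73 = 1.082 at n = 82 and 93/87 = 1.069 at n = 96. At 0.714 SD and 41 per arm, t-test power is 89.2%. Dividing the noncentrality by √1.082, with 74 degrees of freedom, gives 86.6%, a loss of about 2.5 points. Simulation at a slightly larger effect (about 0.72 SD) gave 90.2% and 87.8%.
- *If the factors explain 10% of variance.* Simulated power for t-test and adjusted model is 90.3% and 90.6% under blocks, and 90.8% and 92.0% under minimization.
- *Baseline CIMT alone.* Take equal SDs at both visits and r = 1 − 0.035² / (2 × SD²). The variance ratio (1 + r)/2 is then 0.950, 0.969 and 0.986 for assumed CIMT SDs of 0.078, 0.10 and 0.15 mm. The gain is 1 to 5%.
- *t-test under minimization.* This assumes five binary factors and a 0.8 biased coin. Type I error is 4.1–4.2%, 3.1–3.3% and 2.4% when the factors explain 10, 20 and 30% of variance. The adjusted model stays at 4.9–5.3%.

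**The case against.** The best defence is that the t-test is already primary in substance. Table 1 defines the primary outcome as a rate of change between arms, and D.4.9 takes up the same quantity and attaches the test, alpha and power to it. D.4.10's sentence on group comparison is wide enough to cover a t-test, and its regression is introduced as a study of covariate associations. This makes the t-test the more natural reading, and that stands. It remains an inference: the group-comparison sentence names no outcome or priority, and the model building is prescribed for each specific aim and carried into further analysis.

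A second defence is that the inflation is small. That also stands. With confounding applied, which D.4.10 lists first, the selected model stays within about 5 to 6.5%.

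Three stronger readings are tempting, and the documents do not support them.

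- A reader might infer that the selected regression has replaced the t-test. D.4.10 never says so and never names treatment as a term.
- A reader might blame the 0.20 screen. Alone, it leaves the arm test at about 5%.
- A reader might infer that searching for interactions corrupts the treatment estimate. Chance arm-by-covariate interactions would often be retained, but with centred covariates the arm coefficient still estimates the effect at the covariate mean. Nothing in the plan says that an interaction would be claimed as a treatment finding.

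**Conclusion.** The concern holds as a missing ranking. D.4.9 supplies a test that is valid under blocked randomization, D.4.10 supplies a data-selected regression, and nothing says which one answers Aim 1. It does not follow that the trial lacks a sound primary test or that its error rate is badly inflated.

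The size is modest and conditional on what is reported. Type I error is about 5 to 6.5% if the selected model with a confounder rule supplies the p-value, and up to about 8 to 9% without that rule. It is about 5.5 to 9% if either result may be claimed, and up to about 10% without the rule. It is about 5% if only the t-test is used. These figures rest on assumed covariate numbers, strength and selection thresholds. The gap in the text does not depend on them. The point is worth correcting because the correction is cheap and the result is meant to inform a later trial.

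**What to change.** Name one primary CIMT analysis in D.4.10, before the data are examined, with no data-driven choice of covariates or interactions.

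- **If minimization is used (preferred form).** Use linear regression of annualised change in the mean of left and right CIMT on arm, baseline CIMT and the minimization factors actually used. Report the arm difference with a 95% confidence interval, and keep the D.4.9 t-test as a sensitivity analysis. This requires closing the open list of factors in D.4.6.
- **If allocation is by blocks of four only.** Adjust for baseline CIMT alone, or state in one sentence that the D.4.9 t-test is primary.
- **In either case.** Label the D.4.10 covariate and interaction selection as exploratory, and say that it is not the source of the treatment p-value.

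The cost is wording in D.4.6, D.4.9 and D.4.10. No new data, visits or patients are needed. The adjusted model uses about six degrees of freedom, costs about 2 power points under blocks if no factor is prognostic, and rules out a later choice of covariates. Naming the t-test avoids that cost, but under minimization the test is conservative when the factors are prognostic.

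The direction of subtraction for CIMT change and the place of plaque extent in the primary outcome need separate clarification. Reversing the subtraction does not alter a two-sided p-value.

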## D.5. Specific Aim 3:

- To increase research capability and provide continuous mentorship to Ghanaian co-investigators

**D.5.1.** The SMAART trial will serve as an excellent platform to collaboratively work with the Ghanaian team: *i)* Training and learning on implementation of clinical trials via bi-weekly Skype team meetings). *ii)* Training in scientific manuscript writing for young co-investigators such as [name] and [name] via co-authorship on presentations (n=4) and papers (n=3), and future grants (n=1+). *iii)* Supervised involvement in taking courses in the MUSC CTSA / Center for Global Health web based program in clinical research, which is free for members of grant funded study teams at MUSC and offers courses including *Clinical Epidemiology, Clinical Biostatistics, Regression Methods for Clinical Research, Grants Overview, Critical Review of the Literature, Ethical Issues in Clinical Research and Clinical Trials*.

*iv)* Developing editorial capabilities of [name] via participation in the editorial processes of eNS and ISC. [name] is the Founding Editor-in-Chief of eNeurologicalSci (eNS), a peer review journal of the World Federation of Neurology. He is also chair of the program committee for the International Stroke Conference (ISC), the premier scientific stroke meeting in the world. Participation by Junior Ghanaian co-investigators in these proposed activities will be monitored to build their research experience, foster career development, and enhance networking beyond this specific research project.

## E. ANTICIPATED CHALLENGES

**1) Subject Accrual:** Assessment visits will be scheduled, whenever possible, on days subjects already have scheduled clinic visits or plan to visit the stroke patients who may be incapacitated. **2) Meeting sample size:**

There is a high case load of stroke patients with approximately 700 cases per year. At a recruitment rate of 5 cases per week, recruitment of 120 stroke patients meeting eligibility criteria is a realistic objective. **3) Missing Data:** We anticipate there may be missing data due to loss to follows but we will minimize this by home visits where geographically feasible, providing transportation stipends and employing statistical methodology to account for missing data.

#### F. TIMELINE OF ACTIVITIES:

Activities	YEAR 1				YEAR 2			
	Q1	Q2	Q3	Q4	Q1	Q2	Q3	Q4
Ethics approval and renewal at KNUST and MUSC	X				X			
Hire, orient and train project staff	X							
Data collection instruments & questionnaires	X							
Study subject recruitment and follow-up		X	X	X	X	X	X	X
Training and human capacity building	X	X	X	X	X	X	X	X
Prepare manuscripts, final reports, & grant		X		X		X		X

**F.1. Dissemination:** Yearly reports on progress will be shared with the NIH. Findings from the research study will be disseminated by submitting abstracts and poster presentations at conferences such as the International Stroke Conference and through multiple manuscripts to be published in Open-access journals and results will be disseminated to research participants.

**F.2. Expected Outcomes, Benefits, and Impacts- Translation & Scaling Up:** SMAART will be the first study in Africa to provide pilot data on the safety, feasibility, tolerability, risk factor control rates and intermediate CVD outcome (CIMT) of a polypill strategy for secondary prevention after stroke. The highest risk for recurrent stroke and CVD events occurs within the first year after stroke and the SMAART intervention is targeting this phase to provide prelim data for a future multi-site, multinational study to be conducted across resource-limited centers to evaluate hard CVD events and cost-effectiveness of the polypill, specifically for stroke survivors.
